### **8.1.8 Other concerned data and evaluation indicators**

In addition to collecting concerned data supporting predefined, subjects will be followed up until discharge after cardiac electrical stimulation, and further information will be collected at the same time, during which the follow-up data will be recorded on the CRF.

#### **8.1.8.1 Adverse event**

In addition to SADE, adverse events throughout the study shall be recorded and reported. The potential risks associated with the trial involve major complications of intracardiac electrophysiologic examination.

1. Arrhythmia: Atrial fibrillation is usually transient and does not require any treatment if there is no hemodynamic deterioration. If the subject is intolerant to atrial fibrillation, electrocardiography should be given. When ventricular fibrillation occurs, electrical defibrillation should be given immediately. Complete atrioventricular block occurs if the original bundle branch block is caused by another bundle branch block due to ablation or mechanical damage when the ablation catheter is near the site of the His bundle.
2. Pulmonary embolism: A clot forms in the sheath and rushes into the vein. The femoral artery and femoral vein were overpressurized and bandaged for too long. Prolonged bed rest after surgery, varicose veins in the lower extremities, old age, and hypercoagulability all contribute to venous thrombosis and pulmonary embolism in the lower extremities.
3. Systemic thromboembolism: Thrombus formation or thromboembolism may occur at the catheter entry site.
4. Vagus reflex: Pain, emotional stress, insufficient blood volume and other factors lead to strong reflex dilation of small blood vessels, resulting in decreased blood pressure and rapid slowing of heart rate. The operation time is too long, the fasting time is too long, stimulates the heart and the blood vessel wall; During the process of pulling out the indwelling sheath tube and pressing to stop bleeding, neck compression is too heavy or too long, which may cause vagal reflex.
5. Vascular complications: The formation of pseudoaneurysm means that the injury at the puncture site of the vascular wall cannot be closed, and the blood pressure enters the peripheral tissues to form a local hematoma. The formation of arteriovenous fistula is related to puncture.
6. Bleeding: Bleeding may occur occasionally, especially during femoral operations. The risk of bleeding increases when the femoral artery is used as the catheter approach, especially in obese people.
7. Infection: Invasive operation may lead to local infection of puncture, or in severe cases, systemic infection.
8. Acute pericardial tamponade: This causes hemopericardium if it causes a rupture of the blood vessels in the heart wall or pericardium. If pericardial tamponade is serious, pericardiocentesis for decompression is required.

In addition, the potential risk also involves the safety of the investigational device. Failure to comply with the investigational device safety regulations will not only cause harm to the subjects

and related personnel, but also damage the investigational device and other equipment. The following dangers may arise in the event of improper use:

1. Failure of important device functions
2. Personal endangerment due to electrical impact

## 8.2 Trial flow chart

[figure not shown]

Fig. 3 Trial flow chart

## 8.2.1 Study follow-up plan

Specific follow-up in the study:

1. Baseline assessment
2. During the cardiac electrophysiological examination
3. Assessment on the day of discharge

Follow-up arrangement of the study: see Table 1 for details.

**Table 1 follow-up arrangements of the study**

Contents	Baseline assessment	Intracardiac electrophysiological examination	On the day of discharge
Obtaining informed consent (enrollment)	X		
Demographics, physical condition	X		
Indications of intracardiac electrophysiological examination	X		
Inclusion and exclusion criteria	X		
Drugs	X		
Cardiac electrical stimulation Keep the material related to cardiac electrical stimulation		X	
Evaluation of medical device		X	
Adverse event		X	X

### 1. Baseline assessment

Before enrollment, only subjects who sign the informed consent form and indicate the date are considered to be enrolled, and study-related procedures shall be carried out. The demographic data, indications of electrophysiological examination and medication situation shall be obtained and recorded.

All drugs taken by the subjects that may affect the cardiac pacing or electrical stimulation shall be recorded, including (but not limited to):

Class I – Flecainide and propafenone

Class II –  $\beta$  Receptor inhibitor

Class III – Amiodarone and sotalol

Class IV – Verapamil

## 2. Intracardiac electrophysiological examination

The electrophysiological examination was performed by person authorized by the investigators. Each study site shall use preset parameters (see Figure 4) to perform cardiac electrical stimulation, but for subject's safety, the investigator decides when to terminate the stimulation according to the specific condition of the subject during the operation. Investigators shall keep the materials related to cardiac electrical stimulation, such as downloading or printing the information of cardiac electrical stimulation by multi-channel analyzer.

Adverse events and device deficiencies during the electrophysiological examination shall be recorded.

First aid treatment shall be prepared at the site of cardiac electrophysiological examination, including extracorporeal defibrillators and all other basic first aid equipment and emergency measures for resuscitation / cardiac arrest / asystole.

Programmed extrastimulation (PES)	
(*: The extra stimulus S1S2S3S4 and S1S2S3S4S5 are optional)	
Incremental stimulus S1S1 (atrium or ventricle)	The circumference of the first stimulation is 400-600 MS (determined by the heart rate of subjects), decreased in 50ms, at a time until effective refractory period (ERP).
Extra stimulus S1S2 (atrium or ventricle)	S1: 400-600ms, circumference is determined according to the heart rate of the subject S2= S1-100ms (decreased in 10 ms until ERP)
Extra stimulus S1S2S3 (atrium or ventricle)	S1: 400-600ms, circumference is determined according to the heart rate of the subject S2: S1-100ms S3: S2-50ms (decreased in 10 ms until ERP)
Extra stimulus	S1: 500ms

S1S2S3S4* (atrium or ventricle)	S2: 500ms  S3: 500ms  S4: 300ms (decreased in 10 ms until ERP)
Extra stimulus  S1S2S3S4S5* (atrium or ventricle)	S1: 500ms  S2: 500ms  S3: 500ms  S4: 500ms  S5: 300ms (decreased in 10 ms until ERP)
RS2 stimulus	S2=Sinus RR-50 ms (decreased in 10 ms until ERP)
High rate overspeed stimulation (Burst)	
High rate overspeed stimulation	300ms (at least 10 times)
Sinoatrial node recovery time (SNRT)	
500ms (duration 30s)	
Parameter of Unified stimulus intensity	
Amplitude: 5.0 V, Pulse width: 2ms	

### 3. Follow-up on the day of discharge

Clinical follow-up shall be carried out on the day when the patient is discharged from the hospital in order to observe the short-term effects of electrostimulation for the heart. And all adverse events which have occurred since cardiac electrophysiology examination and until discharge shall be recorded.

### 4. End of the study

The study is completed after the subjects complete the follow-up on the day of discharge. For early termination of the study (e.g. quit, death), the cause and the date of last contact shall be recorded.

## **8.2.2 Device use specification**

The authorized investigators can perform a cardiac electrical stimulation test. First aid treatment shall be prepared at the site of an endocardial electrophysiological examination, including external defibrillator and all other basic first aid equipment and emergency measures for resuscitation /cardiac arrest /asystolia.

## **8.3 Monitoring plan**

As the sponsor of this study, BIOTRONIK is responsible for carrying out appropriate monitoring to ensure that this study can be conducted in accordance with the study protocol and relevant regulations.

BIOTRONIK shall ensure that the device is used under the direct guidance of the investigators. As investigators, the doctors shall comply with applicable laws and the stipulations of National Medical Products Administration, and implement the study in accordance with the signed study agreement and protocol and the requirements of Ethics Committee. Main investigators shall also assume the responsibility for all aspects of the study, including the work of other personnel involved in the study at the center.

The monitors shall be trained, qualified and appointed by BIOTRONIK to monitor the research progress of the study site. The monitors shall visit the study sites at regular intervals during the study. BIOTRONIK may also require company personnel to participate in the monitoring and follow-up process so as to assist the investigators. In regular monitoring, the evaluation of study site includes:

- Required CRF and other applicable research documents are completed and submitted.
- The study site can continue to be monitored.
- Clinical trial protocol is followed.
- Applicable laws and regulations on the responsibilities of investigators and record maintenance are followed

## 9 Statistical Considerations

### 9.1 Statistical design, methods, and analysis procedures

#### 9.1.1 Study hypothesis

The study is a prospective, multi-center, single-group, and target-value-controlled clinical trial. The comparison with the target value proves that the test device meets the requirements of clinical application. The main endpoint index is the success rate of the Qubic Stim cardiac stimulator to send diagnostic electrical stimulation to the heart. The corresponding statistical hypothesis tests are:

$$H_0 : p_T \leq p_0$$

$$H_1 : p_T > p_0$$

Here,  $p_T$  represents the success rate of the test product; and  $p_0$  represents the target value.

#### 9.1.2 Statistical analysis methods

1) Descriptive analysis: Counting data is described by frequency and constituent ratio; while measurement data is described by mean, standard deviation, median, the 25th and 75th quantiles, maximum, and minimum.

2) Baseline demographic analysis: Descriptive analysis will be the main method. For subgroups comparison that may be involved, the likelihood data  $\chi^2$  test will be used between counting data groups. When the theoretical frequency of more than 25% of the cells is less than 5, the Fisher exact probability method will be used. Grouped t-test is used for comparisons between groups with normally distributed measurement data; while Wilcoxon Rank Sum test used for comparisons between groups with non-normally distributed measurement data.

3) Efficacy analysis: All patients who use the investigational product will be included in the analysis. For the primary efficacy indexes, the asymptotic normal method and accurate probability method will be used to estimate the stimulation success rate and its 95% confidence interval, and the lower limit of the confidence interval are compared with the set target values to determine whether the test product meets the needs of clinical application. Meanwhile, the Tipping Point method will also be used to perform a sensitivity analysis on the potential impact of missing data. For the filled data, the asymptotic normal method and accurate probability method are also used to estimate the product success rate and 95% confidence interval, respectively. The statistical analysis method to be used for other efficacy indexes is the same as the baseline; for intra-group

comparisons that may be involved in specific indexes, paired t test is used for comparisons between groups with normally distributed measurement data; while Wilcoxon Rank Sum test used for comparisons between groups with non-normally distributed measurement data; and for intra-group comparison of qualitative indexes, the McNemar paired  $\chi^2$  test is used.

4) Safety evaluation: Adverse events are described by the number and incidence of adverse events; meanwhile, the specific manifestation, severity and relationship between all the adverse events are described in detail.

5) For the main endpoint indexes, statistical analysis will be performed at a significance level of 0.025 on one side (corresponding to the one-sided confidence limit of the 95% confidence interval), and statistical analysis of other indexes will be performed at a significance level of 0.05 on both sides (unless otherwise stated). All the statistical analysis will be run on SAS®9.4 statistical software.

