## **9.2 Calculation of sample size**

### **9.2.1 Total sample size**

The total number of patients enrolled in this study is planned to be 106. The sample size is determined based on a combination of study hypothesis and estimates of expected levels of efficacy, and is calculated on a statistical basis. The sample size is calculated based on the primary endpoint index, *i.e.*, the success rate of Qubic Stim cardiac stimulator to send diagnostic electrical stimulation to the heart. Due to the limited reference materials for similar products, the "*Guidelines for the Technical Review of the Registration of Implantable Cardiac Electrode Lead Products*" combined with the opinions and recommendations of cardiac electrophysiological clinical experts, the target value of the primary index is set at 90%. Meanwhile, assuming that the expected success rate of the investigational product can reach 98%, when the significance level of the statistical test is 0.025 on one side, and the assurance level is 90%, considering the largest possible drop-out rate in the study

is 5%, and using the accurate probability method in combination, the sample size is finally set at 106 cases. The corresponding sample size calculation formula is:

$$n = \frac{[\mu_{1-\alpha}\sqrt{p_0(1-p_0)} + \mu_{1-\beta}\sqrt{p_T(1-p_T)}]^2}{(p_T - p_0)^2}$$

Here,  $p_T$  represents the predicted success rate level of the test product and  $p_0$  represents the corresponding target value;  $\mu$  represents the quantile corresponding to the standard normal distribution,  $\alpha$  corresponds to the type I error level of the statistical test, and it is 0.025 here, while  $\beta$  corresponds to the type II error level of the statistical test, and it is 0.1 when calculation (corresponding to 90% power level).

According to the clinical practice, the estimated screening failure rate is expected to be 20%, so the estimated total number of screening cases is 133.

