## **9.4 Predicted drop-out rate**

In the sample size design process, the largest possible drop-out rate in the study period is expected to be 5%. The drop-out includes all cases that ultimately cannot be included in the main analysis, and usually refers to significant violations of the study protocol judged by the principal

investigator. The possible situations include (not limited to): patients do not meet the inclusion/exclusion criteria; patients do not use any study-related products; patients use third-party products other than the study; patients do not complete follow-up as required; follow-up time windows exceed the set time limit; there are concomitant treatments that affect efficacy. All of the above will be included in the total drop-out rate.

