## **9.5 Qualified/unqualified criteria of the clinical trial results**

From a statistical perspective, judging whether the clinical trial results are qualified or not is equivalent to verifying the initial hypothesis. In this study, the primary evaluation index is the success rate of Qubic Stim cardiac stimulator to send diagnostic electrical stimulation to the heart. By comparing the trial results with pre-set target values, it is confirmed that the test product meets the clinical application requirements.

In summary, the determination of the trial results will be based on the comparison between the test product stimulation success rate and target value. If the results show that the lower limit of the 95% confidence interval of the test product success rate exceeds 90% (a preset target value), a positive result can be considered to indicate that the test product can meet the requirements of clinical application.

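### Two 95% intervals are planned for the primary success rate, nothing says which one decides, and the asymptotic (Wald) one does not hold the one-sided 0.025 level (actual level 0.040 to 0.058)

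*Combined protocol and SAP*

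**What the plan says.** Section 9.1.2, item 3, says that for the primary index "the asymptotic normal method and accurate probability method will be used to estimate the stimulation success rate and its 95% confidence interval". The lower limit is then compared with the target to judge the device. The same pair of methods is applied again to the data set with missing values filled in.

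Item 5 of the same section fixes the error rate: for the primary endpoint, "statistical analysis will be performed at a significance level of 0.025 on one side". Section 9.5 gives the pass criterion: the result is positive if "the lower limit of the 95% confidence interval of the test product success rate exceeds 90" per cent. It names no method.

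Section 9.2.1 says how the trial was sized: "the target value of the primary index is set at 90" per cent, "assuming that the expected success rate of the investigational product can reach 98" per cent, and "using the accurate probability method in combination, the sample size is finally set at 106 cases". That sentence describes the sample size and does not govern the analysis. Section 9.7 leaves only the handling of missing primary data to a later analysis plan, not the choice of interval. Nowhere does the plan rank the two methods, require both to pass, or say what happens if they disagree.

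**The concern.** This is a single-arm registration trial whose verdict rests on one comparison of a lower confidence limit with 90%. Two limits are planned, and the criterion speaks of one. If they fall on opposite sides of 90%, the same data support both a pass and a fail, and the choice would be made after the result is known.

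The two methods are also not equally sound here. The usual asymptotic normal (Wald) interval is too short when a proportion lies near 1, so its lower limit is too high. The question is whether a decision based on it keeps the one-sided 0.025 level at the planned sample size, and whether the two methods really disagree at outcomes that could occur.

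**Working it through.** **Inputs.** Target p0 = 0.90, expected rate pT = 0.98, one-sided alpha 0.025, power 90% and 106 enrolled (section 9.2.1); drop-out 5% (sections 9.2.1 and 9.4). The analysed number is taken as 100 to 106, since 106 × 0.95 = 100.7.

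**Step 1: reproduce 106.** The printed normal formula gives

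n = [1.960 × √(0.90 × 0.10) + 1.2816 × √(0.98 × 0.02)]² / 0.08² = 92.02, so 93.

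Then 93 / 0.95 = 97.9, so 98, which is not 106. With the exact binomial rule (Clopper-Pearson lower limit above 0.90), power at 98% is below 90% for n = 88 to 99 and at least 90% from n = 100 to 129, the largest n checked. Then 100 / 0.95 = 105.3, so 106. The stated figure is therefore reproduced by the exact rule.

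**Step 2: cut-offs.** For x successes in n:

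- Wald lower limit: x/n − 1.96 × √[(x/n)(1 − x/n)/n]
- Exact lower limit: the 0.025 quantile of Beta(x, n − x + 1)

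| Successes / n | Wald lower limit | Exact lower limit |
|---|---|---|
| 100/106 | 89.94% (fail) | 88.09% (fail) |
| 101/106 | 91.25% (pass) | 89.33% (fail) |
| 102/106 | 92.60% (pass) | 90.62% (pass) |
| 94/100 | 89.35% (fail) | 87.40% (fail) |
| 95/100 | 90.73% (pass) | 88.72% (fail) |
| 96/100 | 92.16% (pass) | 90.07% (pass) |

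For example, 101/106 = 0.9528 and 0.9528 − 1.96 × √(0.9528 × 0.0472 / 106) = 0.9125. At every n from 100 to 106, Wald allows 5 failures and exact allows 4. A continuity correction of 0.5/n to the Wald limit does not change the cut-offs in this range.

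**Step 3: actual error rate and power.** With r the smallest passing number of successes, the error rate is P(X ≥ r) for X ~ Binomial(n, 0.90), and power is the same tail at 0.98.

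| n | Wald: r | Wald: error rate | Exact: r | Exact: error rate | Exact: power at 98% |
|---|---|---|---|---|---|
| 100 | 95 | 0.0576 | 96 | 0.0237 | 0.949 |
| 101 | 96 | 0.0542 | 97 | 0.0221 | 0.947 |
| 102 | 97 | 0.0510 | 98 | 0.0206 | 0.946 |
| 103 | 98 | 0.0479 | 99 | 0.0192 | 0.944 |
| 104 | 99 | 0.0451 | 100 | 0.0179 | 0.942 |
| 105 | 100 | 0.0424 | 101 | 0.0167 | 0.940 |
| 106 | 101 | 0.0398 | 102 | 0.0156 | 0.938 |

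Relative to 0.025, the Wald rule runs at 0.0398 / 0.025 = 1.6 times to 0.0576 / 0.025 = 2.3 times the stated level. Accepting whichever interval passes gives the same figures, because Wald passes whenever exact does.

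**Step 4: how often the methods conflict.** They differ only at exactly 5 failures. At n = 106 that outcome has probability 0.9799 − 0.9378 = 4.2% if the true rate is 98%, and 17.8% if it is 95%.

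**The case against.** The strongest objection is that the documents give no formula for the asymptotic method. The only normal-approximation formula printed, in section 9.2.1, uses the variance under the target value, as a score test does, and the matching interval is Wilson's. For n = 100 to 106 the Wilson limit has the same cut-offs as the exact limit, so on that reading there is neither conflict nor inflation. A second benign reading is that both limits must exceed 90%; the exact limit would then govern and the level would hold. Third, section 9.8 lets the analysis proposal be finalised before data lock, and naming the deciding interval could be called a clarification. Fourth, the methods conflict at only one outcome for each n.

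Some of this stands. The range 0.040 to 0.058 depends on the Wald reading, which is the ordinary one, and its upper end requires the analysed number to fall to 100. The power statement also has a limit: at n = 99 or 98 the exact rule allows only 3 failures and power at 98% is 0.863 or 0.866. The per-protocol set, on which section 9.9 also places the primary analysis, could be that small.

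The objections do not remove the defect. Neither the Wilson reading nor the rule that both must pass is written anywhere, and section 9.5, the formal criterion, is silent. Section 9.8 says the main methods will in principle not be changed, which is a reason to settle the rule now. One conflicting outcome per n is enough to raise the error rate from 0.016 to 0.040 at n = 106.

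**Conclusion.** The concern holds. The plan specifies two intervals and one decision and does not link them. If the deciding interval is the Wald interval, or if either may count, the one-sided error rate is 0.040 (n = 106) to 0.058 (n = 100) instead of 0.025. Under the exact interval it is 0.016 to 0.024, with power of at least 0.938 at a true rate of 98%.

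These figures assume that the asymptotic normal method means Wald and that 100 to 106 subjects are analysed. Outside that range the Wald error rate differs, for example 0.087 at n = 93. The absence of a deciding rule depends on neither assumption. Because it affects the trial's only pass criterion, it should be corrected before the data are locked.

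**What to change.** State in sections 9.1.2 and 9.5 that the result is decided solely by the lower limit of the exact (Clopper-Pearson) two-sided 95% interval, which must exceed 90%. Remove the asymptotic interval, or keep it as descriptive only and give its formula. Apply the same rule to the analyses of filled data.

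The cost is a sentence in each section and one fewer allowed failure (4 instead of 5 for n = 100 to 106). No extra subjects are needed: 106 is the number the exact rule gives, and power at 98% stays above 90% as long as at least 100 subjects are analysed. Requiring both limits to exceed 90% would control the error equally well, but with Wald as the other limit it gives the same decisions as the exact limit alone, which is simpler to state.
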